3.1 Primary objective

To demonstrate the non-inferiority of Humylub Ofteno® PF compared to Hyabak® and Lagricel Ofteno® PF in the efficacy of the treatment of patients with dry eye, by means of the OSDI (Ocular Surface Disease Index) test score.

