3.3 Hypothesis

H_0 = The Humylub Ofteno® PF ophthalmic solution is not inferior in its efficacy compared to its comparators, after 30 days of treatment, presenting a 35% decrease in the final score of the OSDI test compared to its initial value in at least 30% of exposed patients.

$$H_0: P_A - P_B \leq \delta$$

H_1 = The Humylub Ofteno® PF ophthalmic solution is inferior in its efficacy compared to its comparators, after 30 days of treatment, as it does not present a 35% decrease in the final score of the OSDI test compared to its initial value in at least 30% of exposed patients.

$$H_1: P_A - P_B > \delta$$

4. Study design

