7.4 Outcome variables

7.4.1 Primary outcome variables

- OSDI score (TE: visits 1 and final).

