7.4.4 Definition of variables, methods and scales to be used for the measurement

Variable	Conceptual Definition	Operational Definition	Measurement Type	Normal value	Statistical test
OSDI Score	OSDI is a questionnaire designed to establish a severity and Classification of dry eye according to its symptoms.	The evaluator will apply the questionnaire to the subject and allow the subject to answer it calmly without any pressure and/or coercion. See annex 16.1 OSDI .	Continuous quantitative	Score: OSDI= $\frac{\sum \text{score}}{25}$ n answers answered	
 • ANOVA of repeated measures. • One-way ANOVA*
TRLNI	Measurement of tear rupture time using non-invasive methods based on the observation of the film's mirror reflection in a grating design or in the placid discs of the corneal topographers and their analysis using specialized software.	The TRLNI will be measured by means of the Oculus Keratograph 5M.	Discrete quantitative	>10s	
 • ANOVA of repeated measures. • One-way ANOVA*
Corneal and conjunctival staining with lysmine green	Detection of epithelial defects in the conjunctiva and cornea.	Direct observation with slit lamp, graduation on Oxford scale. See annex 16.2 Oxford scale .	Ordinal Qualitative	Degrees: The stain is presented in a series of panels (A-E). The points Stains range from 0-5 for each panel and from 0-15 for the exposed toral area of the conjunctiva and cornea.	
 • χ^2 (Chi-square) of Pearson or Fisher's Exacta • McNemar Test*

Corneal and conjunctival staining with fluorescein	
Detection of epithelial defects in the conjunctiva and cornea.
	
Direct observation with slit lamp, graduation on Oxford scale. See annex 16.2 Scale of Oxford.
	
Ordinal Qualitative
	
Degrees: The stain is presented in a series of panels (A-E). The points Stains range from 0-5 for each panel and from 0-15 for the exposed toral area of the conjunctiva and cornea.
	
 • χ^2 (Chi-square) of Pearson or Fisher's Exacta • McNemar Test*

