10.1.2 Data Interpretation

The Kolmogorov-Smirnov and Shapiro Wilk tests will be performed, as applicable, to determine if the distribution of the data is normal in the results obtained in each study group [56].

The results of the continuous quantitative variables will be presented in measures of central tendency: mean, standard deviation, standard error and/or ranges.

- Intra-group analysis: For equal variances, Tukey's POST-HOC test will be used, otherwise the Dunnett statistic will be used. One-way analysis of variance (one-way ANOVA) will be used when applicable.
- Intergroup analysis: Differences between groups will be analyzed using the Repeated Measures Analysis of Variance (ANOVA) test or the Student's t-statistic when applicable.

A non-inferiority margin (δ) of 10% will be used for the primary efficacy endpoint, based on the primary endpoint of the study. The level of difference to consider significance will be an alpha (α) of 0.05 or less.

The result of the nominal and ordinal qualitative variables will be presented in frequencies, proportions and/or percentages.

The statistical analysis to identify significant differences in the qualitative variables will be carried out by creating 2x2 contingency tables and will be carried out as follows:

- Intra-group difference: McNemar test. This is applied to 2x2 contingency tables with a dichotomous feature, with pairs of paired subjects, to determine if the marginal frequencies of row and column are equal (marginal homogeneity) [7].

- Difference between groups: Pearson's X² (Chi-square) test or Fisher's exact test at expected values less than 5.

The level of difference to consider significance will be an alpha (α) of 0.05 or less.

For the reporting of adverse events, all subjects who were randomly assigned to an intervention group after baseline (intention-to-treat population, ITT) will be considered.

The final report of the results will be shown in tables or graphs, as appropriate.

Variable Type	Variable	A1	B1	B2	C1	D1	D2	D3	D4	E1	E2
Background											
A1	Demographic	DT									
Basal											
B1	Medical History/Selection Criteria	DT									
B2	Comprehensive ophthalmological evaluation	DT				TB	T	T	T	TB	TB
Efficiency											
C1	OSDI	DB			B					TB	
Secondary efficacy outcome											
D1	TRLNI				DB	B				TB	
D2	Corneal and conjunctival stains (TVL and TF)		DT	DT			TB			TB	
D3	Conjunctival Hyperemia		DT	DT		TB				TB	
D4	Chemosis		DT	DT		TB				TB	
Safety											

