10.2.2 Justification for sample calculation

Sample size calculation was performed based on the results of the phase IV, multicenter, prospective, double-blind, randomized efficacy and safety clinical study of Humylub Ofteno® PF ophthalmic solution, versus Systane® Ultra and Systane® Ultra preservative free performed in subjects diagnosed with mild to moderate dry eye. The reduction in the mean score of the OSDI test was considered as the main efficacy variable, with a dosage of 1 drop QID. In this study, after one month of treatment, subjects assigned to Humylub Ofteno® PF had a decrease of -49.3% vs -41.3% for Systane Ultra and -48.3% for Systane Ultra PF, with respect to their initial mean values with no statistical differences between treatments ($p>0.05$) [57].

For the present protocol, it is expected that, after 3 days of treatment, 30% of subjects treated with Humylub Ofteno® PF will have a 35% decrease in OSDI score compared to their initial mean value.

The sample size was calculated using the equation for two proportions [58], considering a power of 80% (β), a significance level of 0.05 (α) and a margin of non-inferiority (δ) of 10% and based on the following working hypotheses:

$$H_0: P_A - P_B \leq \delta$$

$$H_1: P_A - P_B > \delta$$

Where, δ is the margin of non-inferiority and, the ratio between the sample size of the two groups is:

$$k = \frac{\eta A}{\eta B}$$

Equations

The calculation to estimate sample size and power was performed using an online tool and following the equations: [59]

$$n_A = kn_B \text{ y } n_B = \left(\frac{P_A(1 - P_A)}{k} + P_B(1 - P_B) \right) \left(\frac{z_{1-\alpha} + z_{1-\beta}}{p_A - p_B - \delta} \right)^2$$

$$1 - \beta = \Phi(z - z_{1-\alpha}) + \Phi(-z - z_{1-\alpha}) \text{ , } z = \frac{P_A - p_B - \delta}{\sqrt{\frac{P_A(1 - P_A)}{n_A} + \frac{P_B(1 - P_B)}{n_B}}}$$

$$k=nA/nB$$

Φ is the standard normal distribution function

Φ^{-1} is the standard normal quantile function

α is a Type I error,

β is the Type II error, which means that $1-\beta$ is the power, and

δ is the test margin.

According to the previous calculation, the result was 50 subjects, this calculation was increased by 20% considering possible losses (10 subjects). The total suggested sample size is 180 subjects (60 cases per arm), which will provide both eyes for the study.

11. Ethical considerations

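### The 10% non-inferiority margin is declared but no planned analysis uses it: the hypothesis and sample size concern a 35%-responder proportion, while the primary analysis tests equality of mean OSDI

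*Combined protocol and SAP*

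**What the plan says.** **Objective and hypothesis.** Section 3.1 aims to show non-inferiority to Hyabak and Lagricel Ofteno PF "in the efficacy of the treatment of patients with dry eye, by means of the OSDI" test score. Section 3.3 makes this a proportion. Under H0 the product "is not inferior in its efficacy compared to its comparators, after 30 days of treatment". The criterion that H0 attaches to this claim is worded as "presenting a 35% decrease in the final score of the OSDI test compared to its initial value in at least 30% of exposed patients". The symbols are H0: P_A − P_B ≤ δ and H1: P_A − P_B > δ.

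**Sample size.** Section 10.2.2: "The sample size was calculated using the equation for two proportions". It takes 80% power, α = 0.05 and δ = 10%, expects 30% of Humylub patients to respond, and arrives at 50 per arm, raised to 60 for losses. No comparator rate is given.

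**Primary variable and tests.** Section 7.4.1 has a single entry: "OSDI score (TE: visits 1 and final". Section 7.4.4 classes OSDI as continuous and assigns "ANOVA of repeated measures" and one-way ANOVA. Section 10.1.2 adds: "Differences between groups will be analyzed using the Repeated Measures Analysis of Variance (ANOVA) test" or Student's t. Qualitative variables get chi-square or Fisher tests.

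**Margin.** Section 10.1.2 says 10% "of 10% will be used for the primary efficacy endpoint, based on the primary endpoint of the study". The synopsis attaches the same 10% to the OSDI score.

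**The concern.** Three parts of the plan describe different questions. The hypothesis and the sample-size formula ask about a difference in responder proportions. The outcome list and the test table ask about a continuous score. The margin is stated for the primary endpoint without saying which of these it measures: percentage points of responders, percent of a mean, or OSDI points.

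The planned tests cannot fill the gap. ANOVA and Student's t test equality of means. If a responder variable were added, chi-square and Fisher would test equality of proportions. None of them refers to δ, which enters only the sample-size and power formulas.

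Section 3.3 makes this worse by labelling non-inferiority as H0, so a non-significant result could be read as success. Neither 3.3 nor 10.2.2 says which product is A. For response proportions, the words and the inequality agree only if A is the comparator.

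Unless the plan is amended first, the scale, the interval and the rule for two comparators would be chosen after the data are seen, in an open-label trial analysed by sponsor staff (10.1.1).

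**Working it through.** **1. Does any analysis use the margin?** The outcome variables in 7.4.1 to 7.4.4 and Table 3 of 10.1.2 list OSDI as a score. A 35%-responder variable appears in neither. No section names a confidence interval or a test against δ.

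**2. The plan's own figure of 50.** The formula in 10.2.2 is

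n = [P_A(1−P_A)/k + P_B(1−P_B)] × [(z₁₋α + z₁₋β)/(P_A − P_B − δ)]²

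Inputs from 10.2.2: α = 0.05 (the printed z₁₋α makes it one-sided, 1.645), power 80% (0.842), margin 10 points, Humylub rate 0.30. I take k = 1 because the arms are equal. My assumptions are A = Humylub, δ = −0.10 (Humylub may be up to 10 points worse), and a comparator rate, since none is given.

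- With P_A = 0.30, n = 50 needs P_B ≈ 0.188: (0.210 + 0.153) × (2.486/0.212)² = 49.9. Humylub would have to be truly about 11 points better.
- For n = 60, P_B ≈ 0.204: (0.210 + 0.162) × (2.486/0.196)² = 59.9, about 10 points better.
- Of the 25 ordered pairs from the percentages in 10.2.2 (49.3, 48.3, 41.3, 35, 30), only 49.3 with 35 gives 50: (0.493×0.507 + 0.35×0.65) × (2.486/0.243)² = 49.99. This is inference only, as the text names no pair. The first figure is a fall in a mean and the second is the responder cut-off, so neither is a responder proportion.

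**3. Equal true rates.** At 0.30 in both arms, n = 0.42 × (2.486/0.10)² = 259.7, so 260 per arm. At 0.40 or 0.60 it is 296.8, at 0.50 it is 309.1, and at 0.70 it is again 259.7. With equal rates the sign of δ does not matter.

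**4. Power per comparison**, Φ(0.10/√(2p(1−p)/n) − 1.645):

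| Common rate | n = 50 | n = 60 |
|---|---|---|
| 0.30 or 0.70 | 0.290 | 0.326 |
| 0.40 or 0.60 | 0.266 | 0.299 |
| 0.50 | 0.260 | 0.291 |

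**5. Both comparators.** The two comparisons share the Humylub arm, so their correlation is 0.5. By the bivariate normal at 0.30 in all arms, power is 0.149 (n = 50), 0.177 (n = 60) and 0.688 (n = 260). For 80% it takes 333 per arm. A simulation of 400,000 trials with Wald 90% intervals gave 0.149, 0.173 and 0.682 at 50, 60 and 260.

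**6. Precision.** The 90% CI half-width at 0.30 is 1.645 × √(0.42/50) = 15.1 points, and 13.8 at 60 per arm. Both exceed the margin, so Humylub would have to be observed about 5.1 or 3.8 points better to pass.

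**7. A non-significant difference cannot stand in for the margin.** If Humylub were truly 10 points worse (assumed 20% against 30%), a two-sided equality test at 0.05 would be non-significant about 79% of the time at 50 per arm and 76% at 60.

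**8. Continuous scale, for comparison.** If the margin meant 10 OSDI points, n = 2 × SD² × (2.486/10)². The documents give no SD. Assumed values of 15, 20 and 25 give 28, 50 and 78 per arm.

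**The case against.** - **The documents are not cleanly split.** Section 10.2.2 also names the reduction in mean OSDI as the main efficacy variable, and the synopsis ties the margin to the score. This is true. It means the mixture of scales also runs inside the sample-size section, which strengthens the point.
- **P_A − P_B against δ is already an estimand with a rule.** Partly fair: 3.3 and 10.2.2 do state that inequality. What is missing is a defined scale, an interval or margin test, and any link to the methods in 10.1.2.
- **The low power figures depend on an assumed comparator rate and on the responder scale.** This stands as a caveat. Without a comparator rate, 50 cannot be called an arithmetic error, and on the continuous scale 50 per arm would suffice if the SD were about 20. But the documents give neither an SD nor a margin in OSDI points.
- **Naming both comparators implies both must pass.** That is the natural reading, but it is not stated as a decision rule or reflected in the power.
- **Section 11.2 allows amendments, so the rule could still be fixed in time.** Agreed, and that is the remedy. The current text does not do it.
- **Some points are slips.** The 3 days in 10.2.2 (against 30 in 3.3) and the reference there to an initial mean value carry little weight alone.

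**Conclusion.** The concern holds, and the plan needs correcting before outcome data are seen. From the text alone, no planned analysis applies the 10% margin, the responder endpoint in the hypothesis is not an outcome variable, and the planned tests address equality. The primary objective therefore cannot be tested as stated.

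The size of the power shortfall is conditional. It assumes the responder scale, one-sided 0.05, a margin of 10 percentage points and equal true rates. For common rates of 30% to 70%, one comparison needs 260 to 310 per arm (rounded up), and has 26–29% power at 50 and 29–33% at 60. At 30% in all arms, power to pass both comparators is about 15% at 50 and 18% at 60. The stated 80% at 50 per arm is reached only if Humylub is assumed to be truly about 11 points better.

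**What to change.** Before outcome data are seen, reconcile 3.3, 7.4.1, 7.4.4, 10.1.2 and 10.2.2, together with the synopsis:

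1. **Choose one primary endpoint and scale.** The option that fits the hypothesis and the formula is the proportion of patients with at least a 35% fall from their own baseline OSDI at the final visit.
2. **State the analysis and rule.** For each comparator, give Humylub minus comparator with a two-sided 90% CI (matching one-sided 0.05). Declare non-inferiority if the lower limit is above −10 percentage points.
3. **State the rule for two comparators:** both must pass, or how each is claimed separately.
4. **Reword the hypotheses.** H0 is inferiority and H1 is non-inferiority; define A and B and match the sign of δ.
5. **Clarify the 30% of exposed patients** as a success criterion or a planning assumption, and reconcile the 3 days and the initial mean value in 10.2.2 with 3.3.
6. **Keep ANOVA or a baseline-adjusted analysis** of continuous OSDI as supportive.
7. **Withdraw or restate 50 per arm for 80% power,** naming the comparator rate assumed.

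If continuous OSDI stays primary, fix a justified margin in OSDI points, a CI rule and a matching sample size with a sourced SD.

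**Cost.** Items 1 to 6 are changes of wording and use OSDI data already scheduled. The real cost is a much less favourable power statement on the responder scale. More patients are not required by this point. For reference, at 30% in all arms, 80% power takes about 260 evaluable per arm for one comparison and 333 for both.

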Conjunctival Hyperemia Changes	
It is defined as the simplest reaction of the conjunctiva to a stimulus, a red appearance is seen secondary to vasodilation of the conjunctival vessels of variable intensity.
	
Direct observation. Classification by Efron scale. See annex 16.3 Efron's scale.
	
Ordinal qualitative
	
Degrees: 0= Normal, 1= Very mild, 2= mild, 3= Moderate and 4= Severe
	
 • χ^2 (Chi-square) of Pearson or Fisher's Exacta • McNemar Test*
Incidence of chemosis	
It is defined as conjunctival edema resulting from an inflammatory reaction. It is classified as present or absent.
	
The evaluator will use a narrow beam of light at 60° and measure whether the conjunctiva separates by $\geq 1/3$ of the total palpebral aperture or whether it exceeds the gray line
	
Ordinal qualitative
	
Present/absent
	
 • One-way ANOVA • Pearson's χ^2 (Chi-square) or Fisher's Exact test
Incidence of AEs	
Any adverse medical event that occurs in a patient or clinical research subject who has been administered a pharmaceutical product and that does not
	
The AEs manifested during the conduct of the study will be collected using the FRCE.
	
Continuous quantitative Categorical qualitative
	
Frequency Subjects presenting EA/total number of subjects exposed. Intensity
 • Mild • Moderate • Severe Causality
	
One-way ANOVA Pearson's χ^2 (Chi-square) or Fisher's Exact test

- Probable
- Possible
- Unlikely

Changes BCVA	Spatial VA is the ability to distinguish separate elements of an object and identify them. It is quantified as the minimum angle of separation (located at the nodal point of the eye) between two objects that allows them to be perceived as separate objects	Snellen chart	Discrete quantitative	Fraction 0.6 to 2.0	ANOVA for repeated measures. • One-way ANOVA*
--------------	-----------------------------------------------------------------------------------------------------------------------------------------------------------------------------------------------------------------------------------------------------------------	---------------	-----------------------	-------------------------------	----------------------------------------------------------------

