7.4.4.5 Corneal and conjunctival fluorescein staining

A drop of topical anesthetic will be instilled in the bottom of the conjunctival sac, then a second drop will be applied to the tip of the fluorescein strip, allowing it to sit on the strip for 5 seconds to elute the dye, shaking off the excess at the end. A small contact of the strip is made with the conjunctiva at the fundus of the temporal sac, while the patient looks upwards, without damaging the conjunctiva. It will be graded according to the Oxford scale. [48]

The PI will record in the file and the FRCE the grade granted for fluorescein staining of DO and OS, respectively.

Management as AE: corneal stains that are equal to or greater than grade III will be considered as AEs.

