7.4.4.7 Conjunctival hyperemia

Conjunctival hyperemia is defined as the simplest reaction of the conjunctiva to a stimulus, with a red appearance secondary to vasodilation of the conjunctival vessels of variable intensity. It will be graduated using the Efron scale. [49] See annex 16.3 Efron's scale.

Management as AS: conjunctival hyperemias classified as grade 3 or higher will be considered as AD.

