E1	Incidence of AD				TB	TB	TB	TB	TB	TM	
E2	MAVC		DB							TM	B

D, Descriptive Statistics; T, 2x2 contingency table; B, Bivariate Analysis; M, Multivariate Analysis.

Table 3. Triangulation of concepts

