16.1 OSDI

OSDI (Ocular Surface Disease Index)

Identification card					
No. of Study: SOPH087-0120/IV	Date: ___ / ___ / ___				
Subject's initials: _____	Subject No.: 087- -				

Directions:

The OSDI test is a simple test created to establish a severity/classification of dry eye according to its symptoms. Answer the following questions by checking the box that best represents your answer:

Over the past week. Have you experienced any of the following alterations?	Frequency				
	In all moment	Almost everywhere moment	50% of the time	Almost nowhere moment	In no moment
1. Light sensitivity	4	3	2	1	0
2. Gritty feeling in the eyes	4	3	2	1	0
3. Eye pain	4	3	2	1	0
4. Blurred vision	4	3	2	1	0
5. Poor vision	4	3	2	1	0

Subtotal of the answered cells

Over the past week. Have you felt discomfort in your eyes with any of the following situations?	Frequency					NA
	In all moment	Almost everywhere moment	50% of the time	Almost in no moment	In no moment	
				Time Moment		
10. Wind	4	3	2	1	0	NA
11. Places with low humidity (dry)	4	3	2	1	0	NA
12. Air-conditioned areas	4	3	2	1	0	NA

Subtotal of the answered cells

[figure not shown]
(B)

Over the past week, Have you had eye problems that have limited you from performing these actions?	Frequency					NA
	In all moment	Almost everywhere moment	50% of the time	Almost nowhere moment	In no moment	
6. Read	4	3	2	1	0	NA
7. Driving at night	4	3	2	1	0	NA
8. Working with a computer or an ATM	4	3	2	1	0	NA
9. Watch TV	4	3	2	1	0	NA

Sum of A+B+C = (D)Subtotal of the answered cells (C)Number of items answered, do not include responses as NA (E)

PANEL	Grade	Criteria
A	0	Equal to or less than panel A
B	I	Equal to or less than panel B, greater than the A
C	II	Equal to or less than panel C, greater than B
D	III	Equal to or less than panel D, greater than C
E	IV	Equal to or less than panel E, greater than D
>E	V	Larger than panel E

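### Oxford and Efron grades are ordinal but go to 2x2 tables and McNemar with no cut-point; ordinal tests on one stated value per patient would close the gap cheaply

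*Combined protocol and SAP*

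**What the plan says.** Section 10.1.2 states that the analysis of the "qualitative variables will be carried out by creating 2x2 contingency tables". Its within-group test is McNemar, of which it says: "This is applied to 2x2 contingency tables with a dichotomous feature". Its between-group test is Pearson chi-square, or Fisher's exact test when expected counts are below 5. The rows for stains and hyperemia in Table 3 carry a code that the legend defines as "T, 2x2 contingency table".

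The variable table in section 7.4.4 classes both signs as ordinal and assigns them chi-square or Fisher plus McNemar. For Oxford staining it says: "Stains range from 0-5 for each panel and from 0-15 for the exposed toral area of the conjunctiva and cornea". The Oxford table in the annexes has six grades, 0 to V, the last being "Larger than panel E". The Efron hyperemia grades are "0= Normal, 1= Very mild, 2= mild, 3= Moderate and 4= Severe".

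The only thresholds on these scales are safety rules. Sections 7.4.4.5 and 7.4.4.6 make corneal staining of grade III or more an adverse event. Section 7.4.4.7 says "conjunctival hyperemias classified as grade 3 or higher will be considered as AD", where AD is evidently the adverse-event abbreviation.

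On eyes, section 7.4.4.5 has the investigator record "the grade granted for fluorescein staining of DO and OS, respectively", and section 7.4.4.6 repeats the sentence for lissamine green. Sections 10.1.3, 10.2.1 and 10.2.2 say that both eyes contribute. No section says whether an analysis row is an eye or a patient.

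**The concern.** A 2x2 table or a McNemar test on a graded sign needs a rule that turns the grade into yes or no, and the plan has none. For staining it is also unclear whether the score is the 0-V grade or the 0-15 total. The analysis of these secondary efficacy signs therefore cannot be run as written.

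Two things are at stake. First, splitting an ordered scale discards information, and how much depends on where it is split. Second, the trial is open-label (section 4.2) and sponsor staff do the analysis (section 10.1.1), so a cut not fixed in advance could be chosen after the data are seen.

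The missing row definition is a lesser matter. It does harm only if two eyes of one patient are entered as two independent observations.

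**Working it through.** **1. Is there a cut anywhere?** Sections 7.4.4 to 7.4.4.8, 10.1.1 to 10.2.2, Table 3 and the annexes were read for a rule that splits the grades. There is none. The number of possible splits is the number of levels minus one: Oxford grade 6 - 1 = 5, Oxford total 16 - 1 = 15, Efron 5 - 1 = 4.

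**2. Does a looser reading of 2x2 help?** If a full grade-by-arm table is meant, Pearson chi-square runs without a cut, but it gives the same answer however the grades are ordered. McNemar, as section 10.1.2 describes it, still needs two categories.

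**3. How much could the choice matter between arms? (illustration)** From the plan: 60 patients per arm, alpha 0.05, chi-square or Fisher. Assumed, because the documents give neither: six grade distributions from mild to moderate, and one odds ratio of 2.2 at every threshold. There were 20,000 simulated trials per row. The last column is the false-positive rate when there is no true difference and the cut with the smallest p-value is reported.

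| Assumed distribution, lowest grade first | Rank test power | 2x2 power, cuts in rising order | Smallest-p false positives |
|---|---|---|---|
| Efron .45 .35 .15 .04 .01 | 0.601 | 0.583, 0.311, 0.027, 0.000 | 0.107 |
| Efron .25 .35 .25 .11 .04 | 0.655 | 0.521, 0.517, 0.249, 0.012 | 0.137 |
| Efron .15 .30 .30 .18 .07 | 0.662 | 0.412, 0.582, 0.379, 0.070 | 0.155 |
| Oxford .35 .35 .18 .08 .03 .01 | 0.635 | 0.575, 0.439, 0.194, 0.011, 0.000 | 0.129 |
| Oxford .20 .32 .26 .13 .06 .03 | 0.660 | 0.490, 0.551, 0.337, 0.116, 0.004 | 0.163 |
| Oxford .10 .25 .30 .20 .10 .05 | 0.667 | 0.309, 0.578, 0.481, 0.245, 0.026 | 0.167 |

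- Rank test: 60-67%.
- Best cut: 52-58%, which is 2 to 13 points lower (0.601 - 0.583 = 0.018; 0.655 - 0.521 = 0.134).
- Worst cut: 0-7%.
- Chi-square on the full grade table, same assumptions: 37-43%.
- Smallest-p cut: 11-17% false positives, against about 5% for the rank test.

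**4. Within one arm (illustration).** Assumed: 60 patients, a 0.4 SD improvement on the underlying scale, and a correlation of 0.5 between visits, with 3,000 runs per distribution. Signed-rank power is 67-80%. McNemar power is 43-47% at the best cut and 0-6% at the worst.

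**5. Eyes as rows (conditional).** With two eyes per patient and inter-eye correlation rho, treating eyes as independent understates the variance by the factor 1 + rho. The true size of a nominal 5% two-sided difference test is 2 x [1 - Phi(1.96 / sqrt(1 + rho))], and the 60 x 2 = 120 eyes per arm are worth 120 / (1 + rho). The documents give no rho, so 0.3 to 0.9 is assumed.

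- rho 0.3: 1.96 / sqrt(1.3) = 1.72, size 8.6%; 120 / 1.3 = 92 eyes.
- rho 0.9: 1.96 / sqrt(1.9) = 1.42, size 15.5%; 120 / 1.9 = 63 eyes.

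If the patient is the row, there is no inflation.

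**The case against.** **The wording may be loose.** The synopsis and the section 7.4.4 table list chi-square or Fisher for these signs without mentioning 2x2, and Table 3 puts the same code on demographics. With three arms, a single 2x2 table could not hold the comparison anyway. This is a fair reading. It removes the need for a cut between arms, but not for McNemar, and it leaves a between-arm test that ignores grade order.

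**The power loss is partly built in.** One odds ratio at every threshold favours a rank test. This stands. With the second and third Efron distributions, the effect placed at one threshold and the grade mix on either side left unchanged (3,000 runs), the 2x2 test at that threshold wins: 52% against 40%, 53% against 38%, and 57% against 47%. But that threshold would have to be known and named in advance, and the plan names none.

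**The error rates concern the wrong question.** A reader might infer that an open cut, or eyes used as rows, makes a false claim of non-inferiority more likely. The documents do not support that. Section 3.2 words these objectives as non-inferiority, but no margin is given for the signs. The 11-17% and 8.6-15.5% figures describe difference tests only. A sponsor hoping to show no difference would also have no reason to seek the smallest p-value.

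**The patient is probably the row.** Sections 10.2.1 and 10.2.2 count patients (180, not 360 eyes), and the McNemar description pairs subjects. This stands. A reader might infer from the references to both eyes that 120 eyes per arm will be analysed as independent. No text says so, and per-eye recording is not stated for hyperemia at all.

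**Conclusion.** The point holds as a low-cost improvement to secondary outcomes, between desirable and recommended. The missing cut is read directly from the text and rests on no assumption. Using ordinal tests removes the need for a cut on either reading of 2x2.

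The size is illustrative. The power gain depends on assumed distributions and a common odds ratio. It ranges from 2 points against the best cut to about 60 against the worst, and it can reverse when the effect sits at one threshold. The figures are for rank tests and do not measure the gain from a baseline-adjusted model. The eye-row inflation is conditional on a reading that the sizing makes less likely.

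The adverse-event thresholds should not be read as the intended analysis cut, because nothing links them to the efficacy tables. The primary OSDI outcome is unaffected. Chemosis is recorded as present or absent and counts as an adverse event, and adverse events are counted per subject, so a per-patient count is already implied. No defect was shown in the tests for non-invasive tear break-up time or visual acuity, and those need no change on this ground.

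**What to change.** In section 10.1.2 and the section 7.4.4 table:

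1. Name the recorded 0-V Oxford grade and the 0-4 Efron grade as the analysed scores. Use one value per patient, the worse eye where both eyes are graded, and state how hyperemia is recorded. The alternative is a method that accounts for paired eyes.
2. Between arms, compare Humylub with each comparator by an ordinal method in place of 2x2 chi-square or Fisher: Wilcoxon rank-sum, or a proportional-odds model adjusted for baseline grade. Report an effect estimate with its confidence interval.
3. Within groups, replace McNemar with the Wilcoxon signed-rank test for these grades.
4. Keep chi-square or Fisher for chemosis, stated as a count per patient.

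The cost is a few sentences and slightly more analysis work, with no extra patients or visits. The worse-eye grade does not use the fellow eye, and the proportional-odds assumption would need checking. This change does not supply the missing margins for the secondary non-inferiority objectives.
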